6.2.1 Screening Evaluation

Screening

Clinicians will complete the “Clinician Referral: Eligibility Checklist” (Supplemental Materials I – CRF Templates) to indicate if a patient may be eligible for the GET Living study. Once potential participants are identified for participation at SCH, a brief screening phone call will be made by a study staff member to confirm general eligibility requirements (see Supplemental Material II for Phone Screening Form). At this point, the research team will conduct a secondary screening assessment to determine if the patient’s scores on the FOPQ and FDI meet cut-offs for the clinical trial.

Screen Failures

Participants will be considered a screen failure if they do not meet all of the inclusion criteria listed in section 4.1 or if they meet any of the exclusion criteria listed in section 4.2.

Consenting Procedure

Before obtaining formal written assent/consent from patients and their parents, clinical providers at the PPMC and Kaiser will obtain verbal consent to be approached by members of the research team.

Study staff, which will include a research coordinator (RC) or postdoctoral fellow trained by [name], will conduct the consent and assent procedure. Eligible participants will be educated about study procedures or any changes in those procedures. Signed consent/assent forms will be kept in a locked filing cabinet in [name] office.

6.2.2 Enrollment, Baseline, and Randomization

Enrollment

Study consenting/assenting and enrollment will take place at the initial study visit. All procedures will be completed by a research coordinator (RC) and/or postdoctoral fellows.

Consenting Procedure for Enrollment

This study will follow the *Informed Consent Process for Research* according to the Stanford University Research Compliance Office. Each participant’s consenting process will be recorded by the study RC in the “Screening and Enrollment Log” (MOOP Supplemental Materials I) within an online REDCap CRF. The signed consent/assent documents will be stored in a locked cabinet in the PI, [name], office.

The informed consent process will take place in a private office, and participants will have the opportunity to choose their seating, read the consent form, and ask any questions they may have

at the beginning of the data collection session. Signed consent/assent forms will be stored in a locked file. Participants will be reminded that their involvement in this study is completely voluntary, and that they can withdraw at any time without any negative repercussions whatsoever (e.g., with regard to clinical care or healthcare access). They will also be explicitly told that they may leave any question blank for questionnaires or unanswered for the clinical interview if they do not feel comfortable answering. See Supplement Material for the consent and assent form.

Non-English Speaking Participants – Individuals who do not speak or understand English will not be recruited to the study. While we recognize the limitations of this approach, practical considerations necessitate the inclusion of only those who are able to speak or understand English.

Enrollment date will be recorded in the “Screening and Enrollment Log” ECRF, which will also include documentation of inclusion/exclusion criteria.

Baseline Assessment (BAS):

During the initial study visit, a baseline biomechanical assessment will be conducted and self-reports questionnaires will be completed by the child and parent.

- Child & Parent Baseline Self-Report Measures:

See Supplemental Materials III for baseline self-report measures

- **Patient Biomechanical Assessment** – Motion analysis will be assessed by [name], PhD, of the Motion and sports Performance Laboratory of Stanford Children’s Health. Gait (stride length and velocity)³⁷, drop jump landing³⁷, and dynamic postural control⁴¹ tasks will be performed by the patient.

Pre-Treatment Baseline Period

During the Pre-Treatment Baseline period, patients will complete the following:

- Child and parent will complete daily diaries collected via REDCap to monitor daily fear of pain, avoidance, acceptance, catastrophizing and pain ratings.
- Actigraphy data will be collected to track daily physical activity and sleep.

The pre-treatment baseline period will last an average of 2-weeks.

See Supplemental Materials III for child and parent daily diaries

Randomization

After a 2-week (on average) pre-treatment daily diary, adolescents will be randomized to either GET Living or TPM and stratified on fear (moderate/high) and disability (moderate/high). A block randomization strategy (**Table 5**) will be used with randomly generated blocks of 2 and 4 to assure near equal distributions across arms as well as to minimize the probability of predicting the next assignment. A randomization spreadsheet with four strata will be created by the study biostatistician, [name].

Table 5. Fear and Disability Stratification

High Fear + High Disability	High Fear + Moderate Disability	High Disability + Moderate Fear	Moderate Disability + Moderate Fear
-----------------------------------	---------------------------------------	---------------------------------------	---

*Fear based on the FOPQ-C; Disability based on FDI – high fear = 50-96; moderate fear = 35-49; high disability = 30-60; moderate disability = 13-29

6.2.3 Blinding

Blinding of treatment arms will not be possible for patients, their parents, and the healthcare professional providing administering active treatment. [name], who will be assessing the biomechanical motion analysis during Baseline and Discharge visits for patients will be blinded to the treatment arm allocation of each patient.

6.2.4 Treatment Measures

The following measures will be collected during Treatment:

- Child Daily Diary
- Parent Daily Diary
- Actigraphy Monitoring

See Supplemental Materials III for child and parent daily diaries

6.2.5 Discharge Session

At the Discharge Session for GET Living or TPM, child and parent will complete self-report measures, along with an exit interview.

- Child & Parent Self-Report Questionnaires Measures:

See Supplemental Materials III for discharge self-report measures

- Patient Biomechanical Assessment – Motion analysis will be assessed by [name], PhD, of the Motion and sports Performance Laboratory of Stanford Children’s Health. Gait (stride length and velocity)³⁷, drop jump landing³⁷, and dynamic postural control⁴¹ tasks will be performed by the patient.

- Exit Interview: patient and parent will be asked questions about their treatment experience.

See Supplemental Materials III for exit interview materials

6.2.6 Follow-Up Assessments

A set of self-report measures will be completed by **all participants** (child & parent) after 3 and 6-months post-discharge.

See Supplemental Materials III for follow-up assessment measures

7. SAFETY ASSESSMENTS

As the study is being conducted within a healthcare facility all normal monitoring of safety will be in place. There are few additional safety risks introduced as part of the involvement in the study procedures. If any risk arises as part of being interviewed, completing measures, or participating in the treatment, there are clinical psychologists and medical personnel immediately available to

assess the situation and provide assistance.

7.1 Specification of Safety Parameters

N/A

7.2 Methods and Timing for Assessing, Recording, and Analyzing Safety Parameters

N/A

7.3 Adverse Events and Serious Adverse Events

For the purposes of this study, the following AE definitions are used:

Adverse Event (AE): Any unfavorable or unintended sign (including an abnormal laboratory finding), symptom or disease temporally associated with treatment interventions, regardless of whether it is considered related to the treatment. AEs are categorized according to the following scale:

Severity Ratings

Adverse Events (AEs) will be rated on the following three-point scale, to determine the severity of:

- **Mild:** An experience that is transient and requires no special treatment or intervention. The experience does not generally interfere with usual daily activities.
- **Moderate:** An experience that is alleviated with simple therapeutic treatments. This experience impacts usual daily activities. Includes laboratory tests alterations indicating injury, but without long-term risk.
- **Severe:** An experience that requires therapeutic intervention unrelated to clinical trial treatment intervention. The experience interrupts usual daily activities. If hospitalization is required for treatment, this will be classified as an SAE.

Relatedness Ratings

Adverse Events (AEs) will be rated on the following three-point scale, to the degree to which the event appears to be related to the study intervention:

- 0, **Unrelated**
- 1, **Possibly Related**
- 2, **Definitely Related**

Expectedness Ratings

Adverse Events (AEs) will be assessed as to whether they were *expected* to occur or *unexpected*, meaning not anticipated based on current knowledge found in the protocol or based on the treating clinician's experience:

- **Unexpected:** the nature or severity of the event is not consistent with information about the condition under study or intervention in the protocol, consent form, or clinician's experience
- **Expected:** the event is known to be associated with the intervention or condition under study.

Unanticipated Problem (UP): an unanticipated problem involving risk to human participants or others, is one that (1) was unforeseen at the time of its occurrence, (2) is related or possibly related to participation in the research, and (3) indicates that participants or others are at an increased risk of harm.

Serious Adverse Events (SAE): Any AE that result in any of the following outcomes:

- Death
- Suicide/Homicide Attempt
- Life-Threatening event
- Event requiring inpatient hospitalization
- Persistent or significant escalation of disability/incapacity

There is no evidence that participation in this treatment trial will increase risk of a serious adverse event (SAE).

7.4 Reporting Procedures

AEs will be identified at any time during participation in this treatment study. Reports of AEs to the Get Living Study team will be assessed and noted. The study team will be informed to notify the PI of any AEs identified during treatment or throughout the duration of enrollment in the study. Parents of patients will also be asked to notify the study team if an AE has occurred. During follow-up contact, the study staff will ask patient and parent if any AEs have occurred since the end of treatment. The known potential risks will be described in informed consent documents and protocol.

All AEs and SAEs will be monitored on a continual basis and documented, by participant, in the respective eCRFS (MOOP Appendices B-C) on REDCap. All AEs and SAEs will also be collated across participants into a Master Sheet for presentation to the Safety Monitoring Committee (SMC) at quarterly meetings. In addition, all SAEs and UPs are reported according to the Stanford Medical IRB reporting guidelines (within 10 working days of occurrence). Follow-up remediation will occur within five days of the IRB's response or decision. All AEs will be reviewed quarterly by the PI and SMC.

SAEs and specific treatment intervention-associated AEs will be reported to the PI, [name], and responsible study staff within 24 hours. All SAEs and UPs will be reported to the NIAMS within 48 hours of the investigator becoming aware of the event. There are no SAEs anticipated for this research study.

7.5 Follow-up for Adverse Events

All AE's will be reported to the IRB of record within five days. Follow-up remediation will occur within five days of the IRB's response or decision.

7.6 Safety Monitoring

Oversight of this clinical trial is provided by the Principal Investigator (PI), [name]. The Study Monitoring Committee (SMC) will involve the following individuals:

- [name] (Medical Expertise) – Mattel Children's at UCLA
- [name] (Clinical Psychology Expertise) – Children's Healthcare of Atlanta
- [name], PT (Physical Therapy Expertise) – Macquarie University

As this is a single-site clinical trial involving low risk, the individuals listed above, along with the PI, [name], and the Stanford University Institutional Review Board (IRB) will be responsible for the duties involved with this DSMP.

8. INTERVENTION DISCONTINUATION

Patients and their parents have the right to withdraw consent/assent or discontinue participation at any time without penalty or any impact on the child's care. Because this is an exploratory clinical trial, we will not discontinue participation based on missed attendance to treatment sessions. There will be no temporary discontinuations from treatment or study participation. The PI may withdraw a patient/parent dyad from the study for one or more of the following reasons:

- Failure to follow instructions of the PI or study staff.
- The PI decides that continued participation would be harmful (e.g., patient reports increased emotional or physical distress from exposure therapy)

Patients and parents will be asked permission to use data collected from the study if they are asked to discontinue or decide to withdraw from the study.

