Feasibility and Acceptability Data. A total of 37 patients (Mean age=13.7; 82% female) enrolled. Of the 34 patients who began treatment (3 dropped out during baseline), 28 completed (18% attrition rate) and 27 have reached 3-months with one lost to follow-up (96% follow-up retention rate). Average duration of treatment for completers was 64 days with an 86% patient daily diary completion rate and 82% for parents. Families also provided feedback at discharge interviews: "My son gained confidence, and I was taught how to support him" (mom), "I can break activities down- it doesn't have

Table 1. GET Living Outcomes

Outcome	Admit	Discharge	3-mos	□2
Adolescent (n=26)				
Pain-related Fear (0-96)	52.2	36.3	30.7	0.36**
Disability (0-60)	24.8	15.8	11.3	0.51**
Pain (0-10)	5.9	4.5	3.7	0.26*
Parent (n=23)^a				
Pain-related Fear (0-52)	37.9	24.5	21.4	0.71**
Protect (0-4)	1.5	1.0	0.8	0.62**

■ Baseline ■ Discharge ■ 3-Month

Figure 2. PHODA-YE Outcomes (n=26)

Note. ^aOne young adult participated without a parent. Two parents did not complete follow up self-reports; **p<0.001; *p=0.001

to be all or nothing" (patient). *Developmentally sensitive modifications*. "The word "worry" was used too often." (mom and dad). Patients also struggled distinguishing between numerical ratings of worry and pain. In response, we developed a rating scale for exposure activities based on **W**: Willingness, **I**: Importance, **L**: Likelihood of Success, and **D**: Degree of Difficulty (**WILD** scale). "Diaries became repetitive" (patient). In response, we created multiple versions of the diaries with items in varying order. Families requested 'coping tools'. In response, we devised exposure action plans (EAP) to increase task persistence (e.g., movement break, music during task).

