8	Graded Exposure with Behavioral Experiments-3	Review HBEs; continuing progressing exposures as appropriate; modify activities and offer support as needed; plan Home Based-Exposures (HBEs)	Parent meets separately with psychologist; discuss strategies for increasing distress tolerance, promoting activity engagement and independence, and conveying confidence in adolescent
9	Graded Exposure with Behavioral Experiments-4	Review HBEs; continuing progressing exposures as appropriate; modify activities and offer support as needed; plan Home Based-Exposures (HBEs)	Parent observes adolescent exposure session, participating as appropriate. Psychology offers further explanation and rationale, as well as support to parent. Psychology provides feedback to parent about any naturally occurring responses to adolescent during exposure.
10	Graded Exposure with Behavioral Experiments-5	Review HBEs; continuing progressing exposures as appropriate; modify activities and offer support as needed; plan Home Based-Exposures (HBEs)	Parent meets separately with psychologist; discuss strategies for increasing distress tolerance, promoting activity engagement and independence, and conveying confidence in adolescent
11	Graded Exposure with Behavioral Experiments-6	Review HBEs; continuing progressing exposures as appropriate; modify activities and offer support as needed; plan Home Based-Exposures (HBEs) *Exposure sessions may occur for 3 – 9 sessions depending on patient needs.	Parent observes adolescent exposure session, participating as appropriate. Psychology offers further explanation and rationale, as well as support to parent. Psychology provides feedback to parent about any naturally occurring responses to adolescent during exposure.
12	Relapse Prevention, Termination & Future Goals	Review HBEs; review general progress and accomplishments; discuss importance of relapse prevention and planning for future; target potential obstacles with Hot Seat cognitive-restructuring and problem-solving activity Review accomplishments; assist adolescent in developing long-term goals; identify “lessons learned” throughout treatment; present graduation certificate.	Joint session: same content.

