Aim 2 Analysis Plan. Satisfaction. We will examine mean satisfaction scores. Adherence/Retention. We will examine mean parent and adolescent adherence to daily diary completion, percent of patients who dropout prior to treatment completion, and percent of sessions completed on-schedule. Health care costs. We will examine mean costs across arms at 3 and 6-month follow-up.

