9.2 Sample Size and Randomization

We chose the largest feasible study size to obtain as precise estimates as possible of improvement in adolescent disability while ensuring adequate power for the treatment difference in the improvement in adolescent pain-related fear. This gave us a starting total sample size of 74 (37 in each arm). Based on pilot data, we expect roughly 19% attrition during treatment to a total of 60 and further attrition to 58 at end of follow-up.

Power calculations were first performed using the simplified approach of paired t-tests for the change from baseline to 3 and 6-months on those with 3 and 6-months data. For this approach, we used means and standard deviations of observed changes in pilot data. We then simulated data from our analytic model using the standard deviations at each time point and standard deviations of change to calculate correlation and hence the random effect and error variances. The mixed models simulation allowed us to use more data and yielded slightly higher power estimates.

Primary Outcome: In our primary power calculation, we assumed that the improvement in adolescent pain-related fear at 3 and 6-months would be 22.4 in GET Living and 5 in TPM, a difference of 17.4, with a standard deviation for change of 21. Under this scenario we will have power of 87% with 58 (29 in each arm) at end of study. Under more conservative assumptions, we still have power of 80% with only 52 at the end of study and a treatment difference of 16.6. With a smaller standard deviation of 18.9, we will have power of 80% with 50 at end of study and a treatment difference of 15.4.

Other Outcomes: For parent pain-related fear, our estimated treatment difference at 3 and 6-months is 13 with an estimated standard deviation for change of 8.5. This would give us power close to 100% for 58 at end of study and we would still have 90% power with a treatment difference of only 8 and only 50 left at end of study.

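### Section 8 lets the PI withdraw a dyad from the study, not only from treatment, with no outcome collection described afterwards; a small bias towards GET Living is possible and cheap to prevent.

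*Combined protocol and SAP*

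**What the plan says.** Section 8 is headed as a rule on stopping the intervention, but its operative sentence concerns the study: "The PI may withdraw a patient/parent dyad from the study for one or more of the following reasons". Two reasons follow: not following instructions, and a PI judgement that continuing would be harmful. The one example of harm is "patient reports increased emotional or physical distress from exposure therapy". The only provision for data is that families are asked for permission to use what has been collected.

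Section 8 also limits losses: "we will not discontinue participation based on missed attendance to treatment sessions".

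Sections 6.1, 6.2.5 and 6.2.6 schedule self-report questionnaires at discharge and, online, at 3 and 6 months. They do not say whether a dyad withdrawn by the PI is still asked for them. Table 6 places the full FOPQ-C at baseline, discharge, 3 months and 6 months only. Section 9.1 analyses it with a linear mixed effects model. Section 9.3 does not separate intention-to-treat from per-protocol populations.

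Section 9.2 plans for losses: "we expect roughly 19% attrition during treatment to a total of 60 and further attrition to 58 at end of follow-up".

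**The concern.** Stopping treatment and ending observation are merged in one rule. A PI withdrawal during treatment would normally leave only the baseline FOPQ-C, or nothing if the family refuses use of its data. The mixed model then in effect predicts the missing outcomes from that baseline and from the GET Living patients who stayed.

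That is harmless if withdrawn patients would have changed like the others. It is not harmless if distress during exposure marks patients whose fear would have stayed high. The named trigger exists in one arm only, so the loss could be selective in that arm and make GET Living look slightly better on the primary outcome. What is at stake is a small shift in the estimate, and only a result close to the significance limit would be sensitive to it.

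**Working it through.** **Inputs from the documents.** 37 per arm; difference 17.4 (22.4 against 5); SD of change 21; 60 left after treatment and 58 at the end (9.2). So (74 − 60)/2 = 7 leavers per arm during treatment and (60 − 58)/2 = 1 later, leaving 29. For scale, the pilot lost 34 − 28 = 6 of 34 (2.2), or 34 − 26 = 8 by the count in 5.4; reasons are not given.

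**Assumptions, not in the documents.** k = 2 to 4 of the 37 GET Living dyads withdrawn by the PI; FOPQ-C visit SD 19 (range 16 to 22); withdrawal correlated 0.5 or 1 with poor average change at 3 and 6 months; all other leavers random; no true difference.

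**Step 1: the plan's power.** A two-sample t-test with 29 per arm, difference 17.4 and SD 21 gives 87.3%; the plan states 87%. Its standard error is 21 × √(2/29) = 5.51.

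**Step 2: which mixed-model contrast the plan uses.** Section 9.2 gives enough for disability to tell: SD of change 11.2 and visit SD 12.6. Error variance is 11.2²/2 = 62.72 and random-intercept variance is 12.6² − 62.72 = 96.04. Power = Φ(difference/SE − 1.96).

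| Contrast | SE | Difference 7 | Difference 8 |
|---|---|---|---|
| Change to one follow-up visit | 2.87 | 68% | 80% |
| Average of 3- and 6-month change | 2.47 | 81% | 90% |
| Stated in 9.2 | | 67% | 79% |

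The single-visit contrast matches, so it is used below.

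**Step 3: the same contrast for FOPQ-C.** Error variance 21²/2 = 220.5; intercept variance 19² − 220.5 = 140.5. With 7 baseline-only patients and 1 lost after discharge per arm, SE = 5.32. The significance limit is 1.96 × 5.32 = 10.4 points.

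**Step 4: bias and error under no true difference.** Bias = (k/37) × (how much worse the withdrawn patients are than predicted). Simulation of the model in step 3, 100,000 trials per cell:

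| Selection | k | Bias (points) | Two-sided error | Falsely favours GET Living |
|---|---|---|---|---|
| none | – | 0.0 | 5.0% | 2.5% |
| correlation 0.5 | 2 | 0.6 | 5.2% | 3.3% |
| | 3 | 0.8 | 5.3% | 3.6% |
| | 4 | 1.1 | 5.5% | 3.9% |
| perfect | 2 | 1.2 | 5.5% | 4.1% |
| | 3 | 1.7 | 5.9% | 4.9% |
| | 4 | 2.2 | 6.8% | 5.9% |

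Over visit SD 16 to 22 the bias runs from 0.4 to 1.3 (correlation 0.5) and 0.9 to 2.6 (perfect). About 0.5 to 1.3 is a fair summary for moderate selection. A harsher variant lets selection act on the very visit being tested: bias 0.8 to 1.5 and two-sided error up to 5.8% at correlation 0.5; 1.6 to 2.9 and up to 8.2% with perfect selection. If TPM loses about half as many poor responders, the bias falls to 0.3 to 0.5 (0.5 to 1.0 with perfect selection).

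**Step 5: could it overturn the planned result?** With k = 4, an observed 17.4 becomes non-significant only if each withdrawn patient is (17.4 − 10.44) × 37/4 = 64 points worse than predicted. From the pilot admission mean of 52.2 less the planned 22.4, the prediction is about 30, so each would have to score about 94 on a 0–96 scale.

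**The case against.** The strongest case against is that the inputs that decide the size are assumed. No section gives a PI-withdrawal rate, the reasons for pilot dropout, or a link between exposure distress and later fear. Section 5.1 says exposure is meant to elicit anxiety, so distress need not mark a poor responder. This stands: the direction is plausible, not shown.

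The plan also contains real limits. PI withdrawal is optional, missed sessions do not end participation, and in Table 2 therapists "modify activities and offer support as needed" and may vary the number of exposure sessions. Families may leave at any time, so some distressed dyads would be lost under any wording. A partial check exists: "Child and parent will complete daily diaries collected via REDCap to monitor daily fear of pain, avoidance, acceptance, catastrophizing and pain ratings" (Section 6.2.2, with diaries continuing through treatment), adverse events are recorded, and Section 9.1 reports the "percent of patients who dropout prior to treatment completion". None of these supplies the missing FOPQ-C at discharge, 3 or 6 months, and the dropout percentage does not separate PI decisions from family decisions.

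A reader might infer three stronger things that the documents do not support:

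- That the rule applies to GET Living alone. Both reasons apply in both arms; only the example is specific to one.
- That Section 9.3 removes withdrawn patients from the analysis. Its most natural reading is a single set of all randomised participants, although it does not say so.
- That the rule could produce a positive trial on its own. Steps 4 and 5 show otherwise.

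**Conclusion.** The point holds as a minor one. Section 8 ends observation along with treatment, and its named trigger can arise in one arm only. The resulting bias towards GET Living is about 0.5 to 1.3 FOPQ-C points with moderate selection and about 1.2 to 2.2 with perfect selection on average follow-up change. It is zero without a link between withdrawal and later fear. Two-sided error stays close to 5% with moderate selection and reaches about 6.5 to 7% only with perfect selection and 4 withdrawn. The chance of falsely favouring GET Living rises from 2.5% to about 3 to 4%, or to 5.5 to 6% in that extreme case. The harsher variant in the working gives somewhat larger figures and leaves the grading unchanged.

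This rests on 2 to 4 PI withdrawals, a visit SD of about 19, and the single-visit contrast inferred from the plan's disability power. It matters only if the observed difference lies near the limit of about 10.4 points.

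**What to change.** Reword Section 8, for example: *The PI may stop study treatment for the listed reasons. Unless consent or assent is withdrawn, the dyad stays in the study and is asked for the scheduled discharge and online 3- and 6-month questionnaires.*

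Report treatment stops and study withdrawals by arm and reason, with PI decisions separate from family decisions.

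If half of the 2 to 4 withdrawn patients respond, the bias falls to about 0.2 to 0.5 points (0.5 to 0.8 with perfect selection). If 80% respond, it is about 0.1 (0.1 to 0.2). These response rates are assumptions.

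The cost is a few extra questionnaires, which families may decline, and an estimated effect that may be slightly smaller. The PI keeps full power to stop treatment for safety.

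Two additions are optional and not needed for this point: a sentence in Section 9.3 that all randomised participants are analysed in their assigned arm, and a sensitivity analysis that moves the predictions for withdrawn patients without outcomes 0 to 25 FOPQ-C points towards worse.
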